6.1. Subject Population

All adult kidney only transplant recipients age 18 years or older at time of the transplant with the diagnosis of DGF will be determined if they are eligible for this study using the criteria described below. This study is not restricted based upon the race or ethnic origin.

6.2. Inclusion Criteria

Inclusion Criteria	
1	Willing and able to provide written informed consent
2	Willing to comply with all study procedures and be available for the duration of the study
3	Male or female, at least 18 years of age
4	Documented diagnosis of DGF or need for dialysis or had dialysis within the first week of kidney transplant
5	Current treatment with tacrolimus based regimen or planned to start tacrolimus based immunosuppressive regimen
6	Females of childbearing potential must have a negative urine or serum pregnancy test prior to randomization and agree to use adequate contraception (hormonal or barrier method of birth control; abstinence) prior to randomization, for the duration of study participation, and for 7 days following completion of therapy. 
 • A female of child-bearing potential is any woman (regardless of sexual orientation, having undergone a tubal ligation, or remaining celibate by choice) who meets the following criteria: 
 ○ Has not undergone a hysterectomy or bilateral oophorectomy; or ○ Has not been naturally postmenopausal for at least 12 consecutive months (i.e., has had menses at any time in the preceding 12 consecutive months).

6.3. ***Exclusion Criteria***

Exclusion Criteria
1. History of hypersensitivity or allergy to any of the study drugs or drugs of similar chemical classes
2. Current use of non-tacrolimus based immunosuppressive regimen or no plan to start tacrolimus based regimen
3. Women who are or plan to become pregnant or breast-feeding during the study period
4. Not suitable for study participation due to other reasons at the discretion of the investigator
5. Major post-surgical complications requiring allograft nephrectomy
6. Multi-organ transplant recipients
7. Non kidney transplant recipients

6.4. ***Subject Screening for Recruitment***

6.4.1. **Subject Identification**

The screening visit will occur within the first week of transplant when transplant nephrology service is consulted for the potential need of dialysis. Basic information about the study will be provided to the patients to assess their interest to participate in the study. All of the recruitment will be performed while patient is still in the hospital after kidney transplant. The following procedures will occur as part of clinical care and will be collected from the subject's medical record:

- Physical exam
- Vital Signs (Temperature, pulse, respirations, and blood pressure)
- Medication History
- Routine labs (CBC, serum pregnancy test for females of child-bearing potential, BMP, or any imaging performed recently)
- Dialysis indicated or not

6.4.2. **Recruitment and Retention Strategies**

A total of 100 patients will be recruited from and enrolled at a single center, the University of Wisconsin Hospital and Clinics. Patients will be recruited and enrolled through the UW hospital inpatient transplant service and will be followed until the recovery of DGF. Based on the demographics of the state of Wisconsin and previous transplant history, more than 80% are expected to be Caucasian, approximately 40% are expected to be female.

6.5. ***Subject Capacity***

Patient's capacity to consent will be assessed by the nephrology provider. If patient is unable to consent for the study, consent to enroll will be obtained only when they are capable of giving informed consent.

6.6. ***Informed Consent***

The PI will be responsible for ensuring that valid consent is obtained and documented for all subjects. Consent will be obtained and documented during an in-person visit.

6.6.1. **Informed Consent Document**

The Informed Consent Document will include the required elements per 45 CFR 46, as well as Good Clinical Practice (GCP) Guidelines.

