Total 100 patients: Obtain informed consent. Screen potential subjects by inclusion and exclusion criteria, review labs and documentation. All patients will have received or will be receiving immediate release tacrolimus as standard of care (SOC)

Visit 1 (Diagnosis of DGF)

Perform baseline assessments.
Medical records and the Transplant Database will be reviewed for the following: Routine blood test, urine test and other radiological investigation based on the clinical judgment. Commonly used test include: CBC, Lyses, BUN, Creatinine, glucose, urinalysis, urine protein/creatinine, immunosuppressive level

Visit 2 (Diagnosis of DGF)

Randomize into Tacrolimus (SOC) or Envarsus XR (study) group

Visit 3 (Daily while inpatient
Or in clinic visit)

Medical records and the Transplant Database will be reviewed for the following: Follow up assessments of study endpoints and safety.
Evaluate for need of dialysis or not. Review routine blood test performed in the morning along with urine output in last 24 hours and examinations to assess the

Visit 4 (recovery from DGF)

Medical records and the Transplant Database will be reviewed for study endpoints and safety, Routine blood test performed, H&P documenting discharged from the DGF clinic

Visit X (Time Point)

Medical records and the Transplant Database will be reviewed for the following:
Interval between transplants to the recovery of DGF
Interval between first and last dialysis
Total number of dialysis
Total number of tacrolimus or Envarsus XR dose adjustment required

2. Key Roles

2.1. *Investigator and Study Center:*

[name], MBBS
Assistant Professor (CHS)
Department of Medicine-Nephrology
[name]
[name]
[name]
[name]
[contact]
Email: [contact]

Principal Investigator:

University of Wisconsin Hospital and Clinics
[name]
[name]

Participating sites:

UW Health-University of Wisconsin Hospital and Clinics
Clinical Laboratories
[name]
[name]

Local Laboratory Services:

[name]
[name]
School of Medicine and Public Health
[name]
Email: [contact]

**ICTR Data Monitoring
Committee Contact:**

[name]
School of Medicine and Public Health
[name]
Ph: [contact]

**ICTR Study Monitoring
Service Contact:**

Veloxis Pharmaceuticals, Inc
[name],
[name]
[contact]

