5.1.1. Primary Study Endpoints

The primary endpoint of the study will be the interval between first dialysis and last dialysis after kidney transplant (duration of DGF).

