5.1.3. Primary Safety Endpoints

Primary safety endpoints include: infections, malignancies, hematological complications including leukopenia, anemia, and thrombocytopenia, cardiovascular complications and events, neuropathy, tremors, gastrointestinal symptoms, uncontrolled hypertension, serious electrolytes abnormalities and immunosuppression-related adverse effects.

6. Study Subjects – Enrollment and Withdrawal

- A total of 100 subjects (50 subjects in each arm) with the diagnosis of DGF will be enrolled over a period of 2 years.
- DGF is defined as the need for a dialysis within the first week of transplant. Once potential DGF patients are identified, the transplant nephrology team will be consulted and the transplant nephrology provider will perform initial evaluation of a patient, discussion with the patient about his/her interest in participating in the research study and inform the research coordinator.
- Subjects will participate in the study until the recovery of DGF as documented by the provider as “discharged from the DGF clinic” or no need for dialysis for more than one week (7 days).
- Subject would be followed for maximum of 3 months. If they still need dialysis beyond 3 months, will be declared as primary dysfunction and will disqualify from the study.

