8.2. Study Visits

8.2.1. Screening/Baseline

At screening/baseline visit transplant nephrology provider will decide about the need of dialysis or not and based on that information will document patient to have DGF or not. In that visit, we will review the patient's medical records. Patient will also be informed about the study and their interest will be gauged. If they are interested, then research coordinator will be informed about the potential subject.

Table 2. Medical chart review of standard of care visits

Visit*	Window	Data collection from medical record and Transplant Database
Day 1 contact	+/- 1 days	H&P, brief updates about research project
Day 3	+/- 0 days	H&P, decision for dialysis, decision to adjust study or SOC dose
Day 5	+/- 0 days	H&P, decision for dialysis, decision to adjust study or SOC dose
Day 7	+/- 0 days	H&P, decision for dialysis, decision to adjust study or SOC dose
Additional visits every 2-3 days until DGF recovery	+/- 0 days	H&P, decision for dialysis, decision to adjust study or SOC dose
Monthly up through Month 3 post diagnosis of DGF	+/- 30 days	H&P, decision for dialysis, decision to adjust study or SOC dose

*visits could be more or less depending upon the timing of DGF recovery for maximum of 3 months post-transplant.

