9.1. Sample Size Determination

Goal is to analyze 100 subjects total (50 in each group), with a goal to decrease DGF duration to less than 10 days in Envarsus XR group from current mean of 13.9 +/- 7 days with tacrolimus based on the power calculation.

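### Inclusion 4 lets a patient be randomised after the last dialysis, with a primary outcome that treatment can no longer change; the dilution is probably small and cheap to prevent

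*Combined protocol and SAP*

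**What the plan says.** - **Eligibility (Section 6.2, item 4).** Three alternatives are joined by or: "Documented diagnosis of DGF or need for dialysis or had dialysis within the first week of kidney transplant". The last looks backwards and is sufficient alone.
- **Definition (Section 6).** "DGF is defined as the need for a dialysis within the first week of transplant". One session meets it, and nothing requires the need to continue.
- **Recovery (Sections 6 and 8.2.3).** Recovery is discharge from the DGF clinic or "no need for dialysis for more than one week (7 days".
- **Primary endpoint (Section 5.1.1).** It is the "interval between first dialysis and last dialysis after kidney transplant (duration of DGF", so the clock starts at first dialysis, not at randomisation.
- **Randomisation (Figure 1, Visit 2, labelled as the diagnosis of DGF).** "Randomize into Tacrolimus (SOC) or Envarsus XR (study) group". No maximum interval from first dialysis is given.
- **Dialysis need.** Section 6.4.1 lists "Dialysis indicated or not" among the items taken from the record at screening. Section 8.2.1 says the "transplant nephrology provider will decide about the need of dialysis or not" and documents DGF on that basis. Neither makes current need a condition of allocation.
- **Analysis set (Section 9.3).** Data from all patients randomised and completed are used.
- **Planning values (Section 9.1).** 50 per arm, to "decrease DGF duration to less than 10 days in Envarsus XR group from current mean of 13.9 +/- 7 days" on tacrolimus.

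**The concern.** Take a patient who has one or two early sessions and then needs no more. That patient qualifies under the past-dialysis route. The recovery rule does not screen the patient out, because someone recruited in hospital and screened in week 1 can hardly have more than 7 dialysis-free days or a clinic discharge yet. Among the listed criteria, only the investigator-discretion exclusion could catch the case. If the last session came before allocation, the first-to-last interval is already fixed, yet the patient takes one of the 50 places per arm and is analysed.

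What is at stake is power. The effect is the same in both arms, so it creates no bias between them, but it shrinks the expected difference in a trial planned without reserve.

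**Working it through.** **Inputs.** From Section 9.1: mean 13.9 days, target 10 (less than 10 taken as 10), so a difference of 3.9; SD 7; 50 per arm. From Section 9.2: significance at 0.05, assumed two-sided. Power is not stated; 80% is assumed. The delay from first dialysis to randomisation is not in the documents, so a range is used.

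**1. Reproducing the plan's figure.** n per arm = 2(1.96 + 0.84)² × 7² / 3.9² ≈ 51. With 50 per arm the standard error is 7 × √(2/50) = 1.4, and 3.9/1.4 − 1.96 = 0.83, giving 79.6% power (78.8% with the t distribution). The stated 50 is reproduced, with nothing to spare.

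**2. Dilution for a given share.** If a share f of each arm is already finished, the expected difference is 3.9 × (1 − f), a loss of 0.39 days for each 10%. Case A keeps the SD at 7. Case B applies the planning values only to patients still on dialysis and puts the finished ones at 0 days, which raises the SD. The source population of the planning values is not stated, so either could apply.

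| f (assumed) | Difference, days | Power, case A | Power, case B | n per arm for 80%, A / B |
|---|---|---|---|---|
| 0% | 3.90 | 79.6% | 79.6% | 51 / 51 |
| 5% | 3.71 | 75.4% | 71.6% | 57 / 62 |
| 10% | 3.51 | 70.8% | 64.0% | 63 / 74 |
| 20% | 3.12 | 60.6% | 50.4% | 80 / 102 |

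**3. How large f might be.** Durations cannot be negative, so use a gamma distribution with the plan's mean and SD: shape (13.9/7)² = 3.94, scale 49/13.9 = 3.53. The share with duration no longer than the delay is the share already finished.

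**4. What restricting entry recovers.** Trials were simulated with 50 per arm and a two-sided t-test. The Envarsus arm gains 3.9 days only in patients still on dialysis at randomisation, and no duration is shortened to before that day. Figures are good to about one point.

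| Delay (assumed) | Already finished | Power, everyone eligible | Power, only those still needing dialysis | Gain |
|---|---|---|---|---|
| 1 to 2 days | 0.03% to 0.3% | – | – | about 0 |
| 3 days | 1% | 75% | 77% | about 2 |
| 5 days | 6% | 70% | 77% | 6 to 7 |
| 7 days | 15% | 60% | 78% | about 18 |

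The 7-day row is the outer edge, and it sits badly with randomisation at diagnosis.

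**5. What the restriction does not recover.** At 3 days only about 1% have finished, yet power is 75% against an undiluted 79%. Without the limit on how far a duration can be shortened it would be 78%. Most of that loss therefore arises in patients still on dialysis, because the clock started before randomisation. An eligibility rule cannot remove it.

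**The case against.** **The number affected may be very small.** Figure 1 puts randomisation at diagnosis, screening is in week 1, and recruitment is in hospital. A reader might infer that some patients will in fact be randomised after their last dialysis. The documents show only that they can be: there is no window, and under Section 6.5 consent may wait for capacity with no time limit there. This objection stands and limits the size of the point.

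**Larger gains are an artefact of the shape.** A normal distribution gives power after restriction of 86% at 3 days and about 87% to 89% at 5 days, so a reader might infer gains well into double figures at short delays. Those powers exceed the undiluted 79%, which removing dilution alone cannot do. The normal shape gives 2.4% impossible negative durations, which is 2.4/6.0 = 40% of the 6% it counts as finished at 3 days. Dropping the short durations cuts the SD to 6.2 at 3 days and 5.9 at 5 days. These gains should not be relied on.

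**Section 8.2.1 does not contradict inclusion 4.** A reader might infer a conflict because 8.2.1 documents DGF from the current dialysis decision. It describes how DGF is recorded at that visit. It does not say that a patient dialysed earlier in week 1 lacks DGF, and the definition in Section 6 covers that patient.

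**These patients are not uninformative.** A reader might infer that they add almost nothing beyond the primary endpoint. Unless discharged earlier from the DGF clinic, they stay on study until more than 7 dialysis-free days have passed, and Section 11.3 collects events for up to 30 days after the last dose. They can contribute on dose adjustments and safety.

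**Enrolling DGF as defined is a legitimate choice.** That is so. The point is that, with this endpoint, the choice spends places on outcomes that treatment cannot affect.

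**Conclusion.** The point holds as a gap in eligibility. The past-dialysis route is sufficient alone, nothing makes current need a condition of randomisation, and the recovery rule and analysis set do not remove patients whose outcome is already fixed. The consequence is dilution that is equal in both arms.

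Its size rests on an assumed delay and an assumed gamma shape. On those assumptions it is close to nil at 1 to 2 days, about 2 points of power at 3 days and 6 to 7 at 5 days. With prompt randomisation it is probably small. It merits a change because the change is cheap and the plan has no spare power. The conclusion concerns the endpoint in Section 5.1.1; Section 9.3 names dose adjustment as the primary analysis, and that discrepancy needs settling separately.

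**What to change.** Reword inclusion 4 along these lines:

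> DGF (dialysis within the first week of transplant), AND documentation by the transplant nephrology provider, at the most recent dialysis assessment before randomisation and before allocation is known, that the patient is not considered to have recovered and that further dialysis is expected or indicated.

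Referring to the most recent assessment matters because dialysis is intermittent, and a same-day requirement would be ambiguous between sessions. The dialysis item in Section 6.4.1 can be used and repeated at Visit 2. Recording it before allocation is known also protects eligibility in an unblinded trial. Patients who no longer need dialysis are logged and not randomised. Dialysis decisions themselves remain with the provider.

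**Costs.**
- Slightly slower accrual: with 1% or 6% excluded, about 100/0.99 = 101 or 100/0.94 = 106 otherwise eligible patients are needed for 100 randomised.
- The result applies to DGF still ongoing at randomisation.
- The control mean rises slightly above 13.9 days (14.0 to 15.3 in the simulations at 3 and 5 days, over both shapes). Section 9.1 should note this.

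**Limits.** A patient expected to need more dialysis may still turn out to have had the last session. The rule complements measuring the endpoint from randomisation and does not replace it. Equally, moving the start of the clock would not cure this gap, because patients already finished would score zero in both arms.

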6.6.2. Process of Consent

Written informed consent will be obtained by the research coordinator or the treatment team member after the potential subject has been presented the information necessary to make a voluntary decision and all questions have been addressed.

6.6.3. HIPAA

Information about study subjects will be kept confidential and managed according to the requirements of the Health Insurance Portability and Accountability Act of 1996 (HIPAA). The elements of the HIPAA Authorization Form will be included in the Informed Consent Document, allowing the use of one document to fulfill both requirements.

6.6.4. Revoking HIPAA Authorization

In the event that a subject revokes authorization to collect or use PHI, the investigator, by regulation, retains the ability to use all information collected prior to the revocation of subject authorization. For subjects that have revoked authorization to collect or use PHI, attempts should be made to obtain permission to collect at least vital status (i.e. that the subject is alive) at the end of their scheduled study period.

6.6.5. Costs to the Subject

There is no extra cost to the patients to be enrolled in the study. Extended release Envarsus XR will be provided through the Veloxis pharmacy for the entire period of the study. Immediate release tacrolimus will fall under the SOC and will be provided through the standard medication distribution system.

6.6.6. Payment for Participation

There are no reimbursements or payments such as cash payments, coupons and gift certificates that the subjects will receive for participation.

6.7. Early Withdrawal of Subjects

6.7.1. Premature termination of study

This study may be temporarily suspended or prematurely terminated if there is sufficient reasonable cause. Written notification, documenting the reason for study suspension or termination, will be provided by the suspending or terminating party to investigator, funding agency, or regulatory authorities. If the study is prematurely terminated or suspended, the PI will promptly inform the IRB and will provide the reason(s) for the termination or suspension.

Circumstances that may warrant termination or suspension include, but are not limited to:

- Determination of unexpected, significant, or unacceptable risk to participants
- Demonstration of efficacy that would warrant stopping
- Insufficient compliance to protocol requirements
- Data that are not sufficiently complete and/or evaluable
- Determination of futility

Study may resume once concerns about safety, protocol compliance, data quality are addressed and satisfy the sponsor, IRB and/or regulatory authorities. Subject's data will be stored in the secure place during this period.

6.7.2. When and How to Withdraw Subjects

If patient is unable to tolerate the study drug Envarsus XR or SOC drug tacrolimus, the subject will be withdrawn from the study, and likely be switched to other immunosuppressive medications for example cyclosporine, or belatacept or any other immunosuppressive medications based on the clinical discretion. Subjects that are withdrawn will be asked to return for one last study visit to conduct the procedures described in the last visit in the protocol.

6.7.3. Data Collection and Follow-up for Withdrawn Subjects

Data for the study purpose will not be collected from subjects who have withdrawn from the study but have active treatment either with SOC tacrolimus or with study drug, Envarsus-XR.

7. Study Agent

Subjects will be randomized to receive (in a 1:1 manner) to either the standard of care arm or the experimental arm:

- Standard of Care: Immediate release tacrolimus
- Experimental: Envarsus XR

This study is exempt from the requirements of an IND based on meeting the criteria defined in the FDA information sheet "[Off-Label and Investigational Use Of Marketed Drugs, Biologics, and Medical Devices](#)".

21 CFR 312.2(b) Exemptions. (1) The clinical investigation of a drug product that is lawfully marketed in the United States is exempt from the requirements of this part if all the following apply:

- (i) The investigation is not intended to be reported to FDA as a well-controlled study in support of a new indication for use nor intended to be used to support any other significant change in the labeling for the drug;
- (ii) If the drug that is undergoing investigation is lawfully marketed as a prescription drug product, the investigation is not intended to support a significant change in the advertising for the product;
- (iii) The investigation does not involve a route of administration or dosage level or use in a patient population or other factor that significantly increases the risks (or decreases the acceptability of the risks) associated with the use of the drug product;
- (iv) The investigation is conducted in compliance with the requirements for institutional review set forth in part 56 and with the requirements for informed consent set forth in part 50; and
- (v) The investigation is conducted in compliance with the requirements of 312.7.

7.1. Starting Dose and Dose Escalation Schedule

Tacrolimus Immediate Release:

Dosing will be per institutional standards at a range from 0.05mg/kg/day to 0.1mg/kg/day in two divided doses by mouth.

Dosage will be adjusted based upon trough levels per the UW Abdominal Transplant Immunosuppression Management Adult-Inpatient/Ambulatory Clinical Practice Guideline. Dosage adjustments will occur after a patient has received 4 doses of the current regimen. Tacrolimus levels will be ordered daily while inpatient and patient has received daily tacrolimus doses (either post-operatively or during readmission)

Once discharged, tacrolimus levels will be monitored as follows:

- Day 0-90: not less than once weekly
- Day 91-180: not less than twice monthly
- Day 181-240: not less than once monthly

Additional monitoring of tacrolimus trough level is warranted if there is a change in medication formulation or patient status that may affect levels or if the creatinine has increased 0.3mgdL above baseline. Levels must be checked within 3-7 days of each dose adjustment and potassium and creatinine levels will be monitored with each tacrolimus level. Additional monitoring is per the UW Abdominal Transplant Immunosuppression Management Adult-Inpatient/Ambulatory Clinical Practice Guideline.

The study team will make all modifications in dosage.

Envarsus XR:

To convert from a tacrolimus immediate-release product to Envarsus XR, administer a once daily dose that is 80% of the total daily dose of the tacrolimus immediate-release product. Tablets should be taken once

daily, preferably in the morning at the same time each day. Tablets must be swallowed whole; subjects must be instructed not to chew, crush or split Envarsus XR tablets. Envarsus XR will be used in the patient population, dose and route of administration that it is FDA approved for, however it will be used in this study as a first line of treatment, rather than a second line of treatment (FDA approved).

Monitor tacrolimus whole blood trough concentrations and titrate Envarsus XR dosage to achieve target whole blood trough concentration ranges of 4 to 11 ng/mL. Measure tacrolimus whole blood trough concentrations at least two times on separate days during the first week after initiation of dosing and after any change in dosage, after a change in co-administration of CYP3A inducers and/or inhibitors, or after a change in renal or hepatic function. When interpreting measured concentrations, consider that the time to achieve tacrolimus steady state is approximately 7 days after initiating or changing the Envarsus XR dose. The study team will make all modifications in dosage.

7.2. *Description/Formulation/Packaging and Storage:*

Tacrolimus (immediate release) will be sourced locally by the institution and handled per standard of care. Immediate release tacrolimus is available in 0.5mg, 1mg and 5mg capsules; bottles all contain 30 capsules. Tacrolimus Immediate release is stored accordingly to the product label.

Envarsus XR will be provided by Veloxis Pharmaceuticals in 0.75 mg, 1 mg and 4 mg tablets; bottles of 30 tablets. Envarsus XR must be stored at controlled room temperature ([15 °C to 30°C] or [59°F to 86°F]).

7.3. *Prior and Concomitant Therapy/ Standard of Care*

The following medications and procedures are permitted during the study:

- Antiemetics, including 5-HT3 serotonin receptor antagonists, may be used at the discretion of the primary provider
- Loperamide or other antidiarrheal should be used for symptomatic diarrhea at discretion of the primary provider.
- Growth factors (eg, granulocyte colony stimulating factor [G-CSF], granulocyte macrophage-colony stimulating factor [GM-CSF], recombinant erythropoietin) are permitted. Their use should follow published guidelines and/or institutional practice.
- Subjects should be transfused with red cells and platelets as clinically indicated and according to institutional guidelines.
- Antiviral therapy, antifungal and antibacterial therapy may be administered if medically appropriate.
- Concomitant treatment with multivitamins, calcium, phosphorus, magnesium supplement will be permitted, as appropriate.
- Hypertensive medications, medication to control blood sugar or pain will be permitted, as appropriate
- Concomitant use of other immunosuppressive medications for induction (example, basiliximab, alemtuzumab or anti-thymocyte globulin) or maintenance (example: mycophenolic acid, steroids) will be acceptable
- Dialysis as indicated
- Kidney allograft biopsy as indicated
- Supportive measures consistent with optimal patient care may be given throughout the study.
- Potentially significant interactions may exist, requiring dose or frequency adjustment, additional monitoring, and/or selection of alternative therapy. Concomitant use with strong CYP3A for inducers and/or inhibitors may alter tacrolimus whole blood concentrations, potential leading to rejection and/or increased toxicity respectively. Tacrolimus whole blood trough concentrations will be monitored closely.
- Grapefruit juice, a CYP3A4 inhibitor may increase serum level and/or toxicity of tacrolimus, subjects must be instructed to avoid.

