3.2. Hypothesis

With extended release Envarsus XR, designed to deliver tacrolimus more consistently, it is hypothesized that there will be less fluctuation of tacrolimus levels requiring less dose adjustment and ultimately early recovery of the DGF.

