5.1.2. Secondary Study Endpoints

The secondary endpoint will be number of tacrolimus or Envarsus XR dose adjustments required during the period of DGF.

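### The dose-adjustment count can favour Envarsus XR without steadier levels, because section 7.1 guides adjustments differently in the two arms

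*Combined protocol and SAP*

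**What the plan says.** Section 7.1 treats the two formulations separately.

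- **Immediate-release tacrolimus.** Dosing is "0.05mg/kg/day to 0.1mg/kg/day in two divided doses by mouth". On timing: "Dosage adjustments will occur after a patient has received 4 doses of the current regimen". On monitoring: "Tacrolimus levels will be ordered daily while inpatient". The target is deferred to a local guideline: "Dosage will be adjusted based upon trough levels per the UW Abdominal Transplant Immunosuppression Management Adult-Inpatient/Ambulatory Clinical Practice Guideline".
- **Envarsus XR.** No number of doses or days is set before a change. The numeric trough target is 4 to 11 ng/mL, with at least two troughs in the first week and after any change. The team is told: "When interpreting measured concentrations, consider that the time to achieve tacrolimus steady state is approximately 7 days after initiating or changing the Envarsus XR dose".

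In section 8.2.1, the chart-review table lists one and the same adjustment decision for study drug and standard of care on Days 3, 5 and 7, and then every 2-3 days until recovery. Section 7.1 gives all dose changes to the study team, and section 7.4 says that the trial is unblinded.

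Section 5.1.2 defines the endpoint: "The secondary endpoint will be number of tacrolimus or Envarsus XR dose adjustments required during the period of DGF". Section 3.2 explains how it is to be read: "it is hypothesized that there will be less fluctuation of tacrolimus levels requiring less dose adjustment". The secondary objective in section 4 concerns steady-state levels, but no endpoint based on measured levels is defined.

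**The concern.** The count serves as a proxy for level stability. That works only if a given out-of-range trough is equally likely to lead to a change in either arm. Under section 7.1, an immediate-release level can be acted on after 2 days. A similar early Envarsus XR level can reasonably be set aside as not yet at steady state. The people who make that judgement know the treatment, and their decisions are the endpoint.

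Randomisation does not help, because the difference arises after allocation. Dividing by days of delayed graft function (DGF) does not help either: it corrects for unequal follow-up, not for unequal readiness to act.

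At stake is the only evidence offered for the secondary objective. Section 9.3 raises the stakes by placing the adjustment count under the primary analysis, against sections 5.1.1 and 5.1.2. That is a separate inconsistency.

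**Working it through.** **The plan's own figure.** No figure is given for the adjustment count. The only one is the sample size in section 9.1: 50 per group, mean DGF 13.9 days, SD 7, target below 10 days. With two-sided alpha 0.05 and 80% power (both assumed, as neither is stated), n = 2 × (1.960 + 0.842)² × 7² / 3.9² = 50.6, or 51 per group against 50 stated. This reproduces the figure but does not bear on the point. The duration and group size are reused below.

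**Waiting time.** 4 doses / 2 per day = 2 days for immediate release. For Envarsus XR the text gives no minimum, so 3, 4 and 7 days are tried as assumptions about behaviour, not as readings of a rule.

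**Ceiling on changes in 13.9 days**, as the whole-number part of 13.9 / wait:

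- 2 days: 13.9 / 2 = 6.95, so 6
- 3 days: 13.9 / 3 = 4.63, so 4
- 4 days: 13.9 / 4 = 3.48, so 3
- 7 days: 13.9 / 7 = 1.99, so 1

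**Simulation with identical stability.** There were 50 patients per arm and 500 trials per setting. From the documents: DGF mean 13.9 and SD 7 days, and the range 4-11 ng/mL. Assumed:

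- gamma-distributed durations, the same in both arms;
- the 4-11 range in both arms, although section 7.1 gives it for Envarsus XR only;
- a level every day throughout DGF;
- daily trough = √44 × exp(b + e), where b is the patient's starting error and e is daily variation;
- an out-of-range level leads to a change once the wait has passed, and each change corrects half of the observed log deviation.

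Only the wait differs between arms. Cells show the share of trials with t-test p < 0.05, then mean changes per patient (immediate release vs Envarsus XR).

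| SD of e, SD of b | 2 vs 2 days | 2 vs 3 days | 2 vs 4 days | 2 vs 7 days |
|---|---|---|---|---|
| 0.2, 0.3 | 5.4% (0.74 vs 0.73) | 4.4% (0.73 vs 0.68) | 11.8% (0.73 vs 0.61) | 49.0% (0.73 vs 0.46) |
| 0.2, 0.5 | 5.4% (1.10 vs 1.09) | 8.0% (1.09 vs 1.00) | 13.6% (1.09 vs 0.93) | 72.2% (1.09 vs 0.68) |
| 0.3, 0.3 | 4.6% (1.80 vs 1.80) | 20.4% (1.80 vs 1.50) | 55.6% (1.80 vs 1.27) | 99.8% (1.80 vs 0.81) |
| 0.3, 0.5 | 5.2% (2.04 vs 2.04) | 21.4% (2.04 vs 1.72) | 64.4% (2.06 vs 1.46) | 100% (2.05 vs 0.95) |
| 0.4, 0.3 | 4.6% (2.86 vs 2.86) | 43.6% (2.87 vs 2.24) | 91.0% (2.86 vs 1.79) | 100% (2.85 vs 1.07) |
| 0.4, 0.5 | 3.4% (3.00 vs 3.00) | 47.8% (3.01 vs 2.36) | 93.4% (3.00 vs 1.91) | 100% (3.01 vs 1.13) |

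Near 5%, the simulation standard error is √(0.05 × 0.95 / 500) = 1 percentage point. Equal waits thus give the nominal rate, which isolates the wait as the cause. The Wilcoxon test shows the same pattern (for example 41-100% at 2 vs 7 days).

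**Variant.** With decisions only at the section 8.2.1 visits and full correction per change (200 trials per setting), the rates were about 5-34%, 15-80% and 39-100% for waits of 3, 4 and 7 days, and 4-6% with no extra wait.

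**The case against.** A reader might infer that section 7.1 locks Envarsus XR doses for 7 days, so that fewer changes are built into the rules. The text does not support that. The 7-day sentence is advice on interpreting a level. The only explicit condition on timing is on the immediate-release arm, and section 8.2.1 offers both arms the same decision every 2-3 days. If the team acts on that schedule without extra delay, the bias can be nil.

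The simulated rates also lean on daily levels throughout. Section 7.1 requires daily immediate-release levels only for inpatients. After discharge it requires them at least weekly up to Day 90, and within 3-7 days of a dose change. A sustained 2-day cycle is therefore a ceiling.

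A reader might also infer that a false positive for the funder's product is the likely result. That is not established. Only Envarsus XR patients undergo the 80% conversion, and any re-titration after it could raise their count. The simulation leaves this out.

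These objections stand as limits on size and direction. They do not rescue the count as a measure of stability: the advice in 7.1 and the schedule in 8.2.1 pull Envarsus XR decisions different ways, and an unblinded team settles the matter patient by patient.

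**Conclusion.** The point holds as a problem of interpretation. The arm-specific guidance can produce fewer Envarsus XR adjustments with no difference in level stability, so the raw count alone cannot support the secondary objective.

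The size is not fixed by the documents. Under the stated assumptions, false significance ranges from about nominal to near certain: 4-48%, 12-93% and 49-100% for Envarsus XR waits of 3, 4 and 7 days against 2 days. These figures show sensitivity to prescriber behaviour and do not forecast the trial's error rate.

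Nor does it follow that the objective cannot be answered at all: sections 7.1 and 8.1 provide for trough levels in both arms. Severity: should-fix. Confidence: moderate.

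**What to change.** 1. Reconcile the two parts of section 7.1 with the section 8.2.1 table, so that the protocol states when a level may lead to a dose change in each arm. The sponsor decides the clinical content; the arms need not share one rule.
2. Define the count as starting at randomisation and excluding the protocol-mandated conversion to Envarsus XR.
3. Record the reason for each change.
4. Assess the steady-level objective with a level-based measure from troughs already collected, such as within-patient trough variability. Keep the adjustment count as supportive, and state that the raw count will not be read as evidence of stability.

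An analysis per eligible decision point would not work as the text stands, because it needs an Envarsus XR waiting time that the protocol does not give.

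The cost is protocol wording and one extra CRF field, with no new procedures. The downside is small: the difference in adjustments may look smaller.
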